Outcomes have been aligned as far as possible with the relevant Brighton/GAIA outcome definitions, and also agreed with those in the MHRA / four nations working group on COVID-19 vaccination in pregnancy and comply with those recommended by the WHO³. See Appendix 2 for full rational and sources of information behind included outcomes, definitions, timings etc. as presented in Table 2.

Both primary and secondary outcomes are of interest, with the former being a composite measure including the associated secondary outcomes, and the latter being a narrower measure or subset of the associated primary outcome, e.g. primary outcome = small for gestational age, secondary outcome = very small for gestational age.

Venous thromboembolism in pregnancy is a standard maternal outcome that may be influenced by infection or vaccination and is not the same as vaccine associated thrombosis with thrombocytopenia (VATT), the condition associated with the AstraZeneca vaccine⁴. Similarly, the pregnancy related bleeding outcome includes disseminated intravascular coagulation (DIC) which can occur in association with massive obstetric haemorrhage: again, this is distinct from VATT. Full lists of ICD10 codes used to identify the maternal outcomes venous thromboembolism, pregnancy-related bleeding, and hypertensive disorders of pregnancy are shown in Appendix 1.

³ <https://www.who.int/publications/m/item/safety-surveillance-of-covid-19-vaccines-in-pregnant-and-breastfeeding-women>

⁴ Pavord, S et al (2021). Clinical Features of Vaccine-Induced Immune Thrombocytopenia and Thrombosis. NEJM. DOI: 10.1056/NEJMoa2109908

'Clean windows' will be applied to outcomes, where appropriate, so that only new or incident cases occurring post vaccination will be counted. Specifically, a clean window of the current pregnancy will be applied for the venous thromboembolism, pregnancy-related bleeding, and hypertensive disorders of pregnancy outcomes (i.e. women will only be included if there is no prior record of these outcomes in the current pregnancy). See Table 2. For both congenital anomalies and pregnancy-related bleeding, further descriptive analyses will be conducted looking at more specific diagnoses within these broader outcome groups if we find evidence for an association between vaccination and these outcomes. For example, for pregnancy-related bleeding, we can further disaggregate into early pregnancy bleeding, obstetric haemorrhage, and DIC.

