Longer term child outcomes, including immune function and infection, and neurodevelopment, will be addressed in future work as required.

Other adverse outcomes that are not specific to pregnant women, will be investigated separately for the whole population as part of wider adverse events monitoring in Scotland. If these analyses suggest any signals in the pregnant population, those outcomes would be investigated in the pregnant population using the COPS data infrastructure, as required.

Table 2: Maternal, pregnancy and neonatal outcome measures for monitoring of safety of COVID-19 vaccination in pregnancy

Outcome measure	Definition	Primary or secondary outcome?	Clean window requirement to identify incident cases	Timing of vaccination to be included	Post vaccination risk period to be examined	Estimated background risk of outcome (%)
Maternal outcomes						
Hypertensive disorders of pregnancy	See ICD10 code list. Note that hypertensive disorders can only be diagnosed at >20 weeks.	Primary	No prior record in this pregnancy	Any	Up to E plus PP	10.0
Venous thromboembolism	See ICD10 code list	Primary	No prior record in this pregnancy	Any	Up to E plus PP	0.15
Pregnancy-related bleeding	See ICD10 code list	Primary	No prior record in this pregnancy	Any	Up to E plus PP	30.0 (for postpartum haemorrhage)
ICU admission or death (any cause)	ICU admission as identified on SICSAG record Death from any cause	Primary	None (but exploration to be undertaken of reasons for any pre-vaccination ICU admission where these are documented)	Any	Up to E plus PP	Unknown
Pregnancy outcomes						
Miscarriage	Miscarriage at <24 completed weeks gestation	Primary	None	Up to 23w+6d gestation	Up to 23+6 gestation	10.0 – 20.0

• First trimester miscarriage	Miscarriage at <14 completed weeks gestation	Secondary	None	Up to 13+6 gestation	Up to 13+6 gestation	Unknown
• Second trimester miscarriage	Miscarriage at 14-<24 completed weeks gestation	Secondary	None	Up to 23+6 gestation	14+0 to 23+6 gestation	Unknown
Ectopic pregnancy	Ectopic pregnancy ending at any gestation	Primary	None	Up to 2+6 gestation	Up to E	1.0
Stillbirth	Spontaneous fetal loss at ≥24 completed weeks gestation Any cause of fetal death Losses related to termination of pregnancy excluded	Primary	None	Any	24+0 to E	0.4
Baby outcomes (live births only unless otherwise stated)						

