In addition, vaccinated pregnant women will also be matched by season of conception (quarter) to historical controls from the pandemic and pre-pandemic periods due to the seasonality of some outcomes. It is not necessary to do this for contemporary controls (from the pandemic vaccination period) as those pairs will be matched by calendar date (i.e. matching a vaccinated woman by maternal and gestational age, on the day of vaccination to a control of the same maternal and gestation age, on the same date).

For comparisons between vaccinated and unvaccinated matched individuals, the index date (reference point for matching maternal and gestational age, and season of gestation for analyses involving controls from historical periods only) will be the date of vaccination.

⁵ Donegan K, King B, Bryan P. Safety of pertussis vaccination in pregnant women in UK: observational study BMJ 2014; 349:g4219 doi:10.1136/bmj.g4219. Available from: <https://www.bmj.com/content/349/bmj.g4219>

The matching strategy for each of the three analyses is shown in Table 5.

Table 5: Matching strategy for each analysis of the matched cohort study

Analysis	Time period for control group*	Matched three controls to each case by:	Notes
Primary analysis	Pre-pandemic period (01 January 2015 to 29 February 2020)	
 Maternal age Gestational age Season of conception (quarter) 	
 Aim to match to three unvaccinated controls Maternal age matched by ± 1 year but relaxed at tails of maternal age distribution Gestational age matched by same week but relaxed at tails of the gestation distribution
Supplementary analysis 1	Pandemic vaccination period (from 08 December 2020 to date of data extraction), excluding cases and controls with confirmed COVID-19 between six weeks preconception to end of outcome-specific follow-up period	
 Maternal age Gestational age 	
Supplementary analysis 2	Pandemic vaccination period (from 08 December 2020 to date of data extraction), including cases and controls with confirmed COVID-19 between six weeks preconception to end of outcome-specific follow-up period	
 Maternal age Gestational age 	

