*Note that only women who have been followed-up to the end of the outcome-specific follow-up period at the end of each study period (i.e. 29 February 2020 for pre-pandemic controls and data of data extraction for pandemic controls) are eligible to be controls for a given outcome analysis.

3.7: Power calculation for matched cohort

It is estimated that by the end of 2021, full outcome and follow-up data will be available for approximately 5,000 vaccinated pregnant women, and by end of 2022, data available for 10,000 vaccinated pregnant women⁶.

Outcomes can be grouped as frequent (risk approximately 10%), moderate (approximately 3%), and rare (approximately 0.5%). Risk estimates for each adverse outcome are provided in Table 2. Based on these estimates and assumptions, with the relative risk of an event occurring post-vaccination set at 0.5, 1.2 and 2.0, and with statistical significance set at 0.05 and 0.01; power calculations for the various scenarios were calculated and are shown in Table 6. The power to detect a relative risk of 0.5, based on 5000 vaccinated pregnant woman against 15000 controls (ratio 1:3), when estimated

⁶ Personal communication with [name], July 2021.

adverse event occurrence is 0.5%, is 94%. This means that the study has a 94% chance of having a p-value of less than 5% (a statistically significant result and strong evidence against the null hypothesis) if there is really a difference in risk between vaccinated and unvaccinated women.

If the statistical power is low, the study sample size may be too small to detect any differences (i.e. under-powered) and therefore null results will need to be interpreted with caution. By convention, 80% is an acceptable level of power. It is acknowledged that the study may be under-powered to identify rarer outcomes.

Table 6: Power calculations scenarios

Cases	Controls	Estimated risk	Relative risk	Power %
5000	15000	0.50%	0.5	94
			1.2	10
			2.0	66
		3.00%	0.5	100
			1.2	45
			2.0	100
		10.00%	0.5	100
			1.2	94
			2.0	100
10000	30000	0.50%	0.5	100
			1.2	17
			2.0	94
		3.00%	0.5	100
			1.2	75
			2.0	100
		10.00%	0.5	100
			1.2	100
			2.0	100

4.0: Data Analyses

4.3: Descriptive analyses

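### For miscarriage, the section 3.7 power calculation makes no allowance for risk already passed at the matched week of vaccination

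*Protocol*

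**What the plan says.** Section 3.7 sorts outcomes into three risk tiers (about 10%, 3% and 0.5%) and refers to Table 2 for the underlying figures: "Risk estimates for each adverse outcome are provided in Table 2. Based on these estimates and assumptions". It then computes power "with the relative risk of an event occurring post-vaccination set at 0.5, 1.2 and 2.0". For 5,000 vaccinated women and 15,000 controls, Table 6 prints 94% in the 10% tier at a relative risk of 1.2. For 10,000 and 30,000 it prints 100%.

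In Table 2 the primary miscarriage outcome is "Miscarriage at <24 completed weeks gestation", with a background risk of 10–20%. Vaccination up to 23+6 weeks is included, and the last column but one is headed as a post-vaccination risk period.

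Section 3.6 matches each vaccinated woman to three controls on maternal age and on gestational age in the same week. The index date for that matching "will be the date of vaccination". Under section 3.5.2 the exposure window opens six weeks before conception.

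**The concern.** A woman vaccinated during pregnancy is still pregnant on that day, and matching on gestational week puts the same condition on her controls. Neither can contribute a miscarriage before the index week. The event risk that sets power is therefore the risk remaining after that week, averaged over the weeks at which women were vaccinated. It equals the Table 2 figure only for women vaccinated before losses begin, including those vaccinated before conception, and it falls towards zero near 23 weeks. The power input and the analysis have different time origins.

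Miscarriage is a primary outcome, and section 3.7 acknowledges low power only for rarer outcomes. A reader of Table 6 could take a null miscarriage result at 5,000 women as near-conclusive against a 20% relative increase.

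**Working it through.** **Reproducing Table 6.** The test is a pooled-variance two-proportion z test, two-sided 5% (sidedness is not stated; two-sided is assumed), with a 1:3 ratio:

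power ≈ Φ[(|p1 − p0| − 1.96·s0)/s1], where s0 uses the pooled risk and s1 the separate risks.

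All 18 cells reproduce within 2 points if the vaccinated risk is p0/RR. For p0 = 10%, RR 1.2 and n = 5,000:
- p1 = 8.33%, pooled risk 9.58%, s0 = 0.00481, s1 = 0.00461
- (0.01667 − 0.00942)/0.00461 = 1.57, so power is 94.2%, against 94% printed

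With the usual reading, vaccinated risk = RR × control risk, only 9 of 18 cells reproduce and this cell gives 97.5%. That reversal is a separate matter. Both directions are shown below so that each result can be set against its own baseline (94.2% or 97.5%).

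**Remaining risk.** Let T be the whole-pregnancy risk and F(g) the cumulative loss by week g. The risk remaining at week g is (T − F(g))/(1 − F(g)).

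**Assumptions, none of them in the documents.** 80–90% of losses are spread evenly over weeks 4–14 and the rest over weeks 14–24. Conception is at gestational week 2, so six weeks preconception is week −4. Vaccination is spread evenly over a stated window. T covers the Table 2 range.

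**Example.** T = 10%, 80% of losses early, vaccinated at 9 weeks: F = 10% × 0.8 × 5/10 = 4%, and the remaining risk is 6/96 = 6.25%. At 14 weeks F = 8%, and it is 2/92 = 2.2%.

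**Full exposure window** (week −4 to 24), RR 1.2, 5,000 vaccinated:

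| T | Mean remaining risk | Power, vaccinated = p/1.2 (Table 6 direction) | Power, vaccinated = 1.2 × p |
|---|---|---|---|
| 10% | 5.1–5.5% | 68–71% | 78–81% |
| 15% | 7.7–8.3% | 86–89% | 92–94% |
| 20% | 10.4–11.2% | 95–96% | 98–99% |

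At 10,000 vaccinated and T = 10%, power is 93–95% in the Table 6 direction and 97–98% in the other.

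**If vaccination was later**, RR 1.2, 5,000 vaccinated, Table 6 direction:

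| Vaccination window | T = 10% | T = 20% |
|---|---|---|
| 2–24 weeks | 54–59% | 86–91% |
| 6–24 weeks | 37–45% | 69–79% |
| 12–24 weeks | 14–23% | 28–46% |

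At 10,000 and T = 10%, the last two windows give 65–75% and 25–42%.

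**Without the loss-curve assumption.** In the Table 6 direction, power at RR 1.2 drops below the protocol's 80% benchmark once the analysed risk is under 6.6% (5,000) or 3.4% (10,000). In the other direction the thresholds are 5.3% and 2.7%.

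**Other relative risks.** For RR 0.5 and 2.0, power stays at 99.9% or more for any analysed risk down to 2%. At 1% the lower of the two is 94.2% with 5,000 vaccinated.

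**The case against.** The strongest reply is that 10% is the bottom of the protocol's own 10–20% range and may already be cautious. This stands. At a whole-pregnancy risk of 20%, with vaccination over the full window, the remaining risk is still 10.4–11.2% and the printed 94% holds. At 15% the shortfall is modest. A reader might infer that the 10% tier overstates the miscarriage risk analysed; the documents do not show that.

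The lowest powers come from windows that leave out women vaccinated before conception. The primary analysis includes them, and section 3.6 removes them only in a sensitivity analysis. Those rows show sensitivity and are not forecasts.

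Table 6 is a generic grid with no row labelled miscarriage, and it already has a 3% row showing 45% at RR 1.2. That is fair, but section 3.7 sends the reader to Table 2 for each outcome's risk, and a figure of 10–20% leads to the 10% row.

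Section 3.5.1 describes women as at risk of miscarriage from conception. This does not restore the lost risk, because a woman vaccinated in pregnancy, and her control matched on week, have already survived to the index week.

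Two wider readings fail. The clean-window rule, "so that only new or incident cases occurring post vaccination will be counted", is not evidence here, because Table 2 lists no clean window for miscarriage; the point rests on the matching and the index date. Nor does the argument carry over to pregnancy-related bleeding or venous thromboembolism. The 30% for bleeding is a postpartum haemorrhage figure, so those events follow any vaccination in the exposure window. The 0.15% for thromboembolism already lies below the lowest tier, and weak power for rare outcomes is acknowledged.

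Finally, power does not set the sample size here, and confidence intervals will be reported. This limits the consequence to how a null result is read.

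**Conclusion.** The point holds for miscarriage at a relative risk of 1.2, mainly at 5,000 vaccinated women. Section 3.7 uses a whole-pregnancy risk where the matched design analyses the risk remaining after the index week, and it makes no adjustment. On the stated assumptions and the full exposure window, the printed 94% becomes about 68–71%, 86–89% or 95–96% for whole-pregnancy risks of 10%, 15% and 20%. It is lower if vaccination was mostly later in pregnancy. At 10,000 the effect is small unless vaccination was mostly later. The entries for relative risks of 0.5 and 2.0 barely change unless the analysed risk falls well below 2%.

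The 94% is therefore unsupported for miscarriage, not proven wrong. The size depends on the distribution of vaccination week and on the loss curve, neither of which the protocol gives. The number of vaccinated women is held at 5,000 or 10,000 throughout.

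**What to change.** For miscarriage only, replace the whole-pregnancy risk in the power calculation with the risk remaining after the index week. Take it from the January 2015 to February 2020 COPS pregnancies and weight it by the observed gestational week of vaccination, which section 4.3 already plans to describe. Restate miscarriage power at a relative risk of 1.2 in section 3.7 and Table 6, so that a null result at 5,000 women is not read against 94%.

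The cost is one tabulation of data already held and a few revised figures. The stated miscarriage power may become less favourable. The design and the analysis do not change.

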Characteristics (e.g. covariates) of the vaccinated and unvaccinated cohorts (from the pre-pandemic and pandemic vaccination time periods), and of the number and risk of all outcome events in the vaccinated and unvaccinated groups will be described to assess the comparability of the groups and to provide better understanding of the data. Summary statistics on the dose, type and class of vaccination in the vaccinated population will be described. Median, range and inter-quartile range of the gestational week of vaccination will be calculated.

Summary statistics and plots of time from vaccination (or matching) to date of outcome will be conducted to provide additional contextual information and to explore plausibility of gaps or clustering of the outcomes in time. As this will not be a time-to event analysis, it will be important to explore descriptively whether there are differences in the temporal trends of the outcomes by vaccination status.

Summary tables of the number and risk of each outcome in the vaccinated and unvaccinated pregnant cohorts, overall, by covariates, and by vaccine type, class, dose number, will be produced.

4.4: Statistical analyses

Maternal, pregnancy and neonatal outcomes in the vaccinated and unvaccinated pregnant cohorts will be compared using conditional logistic regression, where possible. This model type is used to account for matching. Odds ratios (ORs) with 95% confidence intervals will be produced for each comparison and a correction for multiple testing applied (e.g. Benjamini and Hochberg).

The exception will be for pregnancy outcomes where there is a competing risk (i.e. each woman can only have one of these outcomes), such as miscarriage, ectopic pregnancy, termination of pregnancy, stillbirth, and live birth. These will be examined using conditional multinomial logistic regression. The reference for each comparison when examining pregnancy outcomes will be live births (or ongoing pregnancies at a relevant gestation when studying early pregnancy outcomes only). Age, gestational week and season/quarter (when included in the matching strategy) will also be included in the model to account for matching. Termination of pregnancy is not an outcome of interest but it will need to be included in models as a competing risk.

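### Table 6 shows power only at two-sided, uncorrected 0.05: the announced 0.01 results are absent, and no figure reflects the planned multiple-testing correction

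*Protocol*

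**What the plan says.** Protocol section 3.7 sets the inputs: background risks ("Outcomes can be grouped as frequent (risk approximately 10%), moderate (approximately 3%), and rare (approximately 0.5" per cent), effects ("with the relative risk of an event occurring post-vaccination set at 0.5, 1.2 and 2.0"), and two significance levels ("and with statistical significance set at 0.05 and 0.01"). It then states that "power calculations for the various scenarios were calculated and are shown in Table 6".

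Table 6 has a single power column with one value for each of 18 scenarios and no significance level in its header. The worked sentence for the first row reads: "This means that the study has a 94% chance of having a p-value of less than 5" per cent, "if there is really a difference in risk between vaccinated and unvaccinated women". Section 3.7 also sets a benchmark: "By convention, 80% is an acceptable level of power".

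Section 4.4 says that the odds ratios will be produced with "a correction for multiple testing applied (e.g. Benjamini and Hochberg"). Section 3.7 makes no allowance for this.

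**The concern.** Two statements do not agree with Table 6. Results at two significance levels are announced, but only one set is printed. And the rule in the worked sentence, p below 5%, is not the rule that will decide significance once the section 4.4 correction is applied.

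Section 3.7 ties the reading of null results to power and gives 80% as the acceptable level. In a safety study, readers will use Table 6 to judge which null findings are informative. Where a cell's power depends on the threshold, a figure at uncorrected 0.05 is the most favourable one, and the table does not say so.

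**Working it through.** **Inputs.** From section 3.7 and Table 6: 5,000 vaccinated against 15,000 controls, or 10,000 against 30,000; risks 0.5%, 3% and 10%; RR 0.5, 1.2 and 2.0; levels 0.05 and 0.01. Sidedness is not stated; I take two-sided, because the text speaks of a difference and uses RRs on both sides of 1. Table 2 lists 15 primary and 8 secondary outcomes.

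**Formula.** Two independent proportions, pooled variance under the null, with p1 the vaccinated risk and p2 the control risk:

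- pbar = (n1·p1 + n2·p2)/(n1 + n2)
- SE0 = √[pbar(1 − pbar)(1/n1 + 1/n2)]
- SE1 = √[p1(1 − p1)/n1 + p2(1 − p2)/n2]
- power = Φ[(|p1 − p2| − z·SE0)/SE1]

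z is 1.960 at 0.05, 2.576 at 0.01 and 2.935 at 0.05/15 = 0.0033.

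**Step 1: reproduce the printed 94%** (5,000 vaccinated, 0.5%, RR 0.5).

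- RR as written: p1 = 0.5 × 0.005 = 0.0025, pbar = 0.004375, SE0 = 0.001078, SE1 = 0.000911. At 0.05, (0.0025 − 1.960 × 0.001078)/0.000911 = 0.425, so power is 66.5%, not 94%.
- RR inverted: p1 = 0.005/0.5 = 0.010, pbar = 0.00625, SE0 = 0.001287, SE1 = 0.001520. At 0.05, (0.005 − 1.960 × 0.001287)/0.001520 = 1.63, so power is 94.8%, which matches.

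**Step 2: all 18 cells.** I count a match as within 2 percentage points. With RR inverted, 18 of 18 match at two-sided 0.05 and 10 of 18 at 0.01. Those ten are the cells printed as 100, which cannot tell the two levels apart; none of the eight cells printed below 100 matches 0.01. With RR as written, 9 of 18 match at 0.05. Table 6 is therefore a 0.05 table with the RR inverted.

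**Step 3: change only the threshold.** Power (%) at 0.05 / 0.01 / 0.05/15:

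| Vaccinated | Risk | RR | Printed | RR inverted (as in Table 6) | RR as the text defines it |
|---|---|---|---|---|---|
| 5,000 | 0.5% | 0.5 | 94 | 94.8 / 86.6 / 78.9 | 66.5 / 38.1 / 23.3 |
| 5,000 | 0.5% | 1.2 | 10 | 10.1 / 2.7 / 1.1 | 14.4 / 4.9 / 2.3 |
| 5,000 | 0.5% | 2.0 | 66 | 66.5 / 38.1 / 23.3 | 94.8 / 86.6 / 78.9 |
| 5,000 | 3% | 1.2 | 45 | 44.7 / 21.9 / 12.4 | 55.5 / 32.6 / 21.3 |
| 5,000 | 10% | 1.2 | 94 | 94.2 / 82.4 / 71.0 | 97.5 / 91.4 / 84.6 |
| 10,000 | 0.5% | 0.5 | 100 | 99.9 / 99.3 / 98.5 | 94.1 / 79.8 / 65.8 |
| 10,000 | 0.5% | 1.2 | 17 | 16.9 / 5.5 / 2.4 | 23.3 / 9.4 / 4.8 |
| 10,000 | 0.5% | 2.0 | 94 | 94.1 / 79.8 / 65.8 | 99.9 / 99.3 / 98.5 |
| 10,000 | 3% | 1.2 | 75 | 74.5 / 50.6 / 36.0 | 83.4 / 64.9 / 51.5 |

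With RR as the text defines it, the other nine cells stay above 99% at all three thresholds.

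Reading along a triplet gives the effect of the threshold. The step from the printed value to the first figure of the last column is the RR-direction error, a different matter.

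**Step 4: against the 80% benchmark.** Thirteen cells print at 80 or more. With RR as the text defines it:

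- eleven stay at or above 80% at 0.05/15 (lowest 84.6);
- one (5,000, 0.5%, RR 0.5) is already below at 0.05, because of the RR direction;
- one (10,000, 0.5%, RR 0.5) is taken below by the threshold: 94.1 to 79.8 to 65.8.

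In Table 6's inverted direction, three cells printed 94 cross by 0.05/15: to 78.9, 71.0 and 65.8.

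**Step 5: why a range.** Benjamini-Hochberg compares the i-th smallest of m p-values with 0.05·i/m. The effective threshold runs from 0.05/m, when a signal stands alone, to 0.05, when every test is rejected. Power lies between the two corresponding columns.

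**The case against.** Five points can be made for the plan.

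- Power per comparison at 0.05 is a legitimate planning quantity, and the worked sentence openly defines it that way. That stands for the sentence, but it does not supply the 0.01 results or say that the figures precede the correction.
- The method is given only as an example and the family is not named; an analysis plan not seen here may settle both. This stands. A reader might infer that each outcome must reach 0.0033, but the protocol does not support that: 0.05/15 is a floor under an assumed family. Several outcomes also overlap, such as preterm and spontaneous preterm birth, so a real effect may not appear alone.
- A reader might infer that the correction undermines most cells that look adequately powered, or that every printed figure is too high. Neither holds. In the stated RR direction one such cell crosses 80% through the threshold, and the printed 66 for 5,000, 0.5%, RR 2.0 is below its power even at 0.05/15 (78.9).
- The protocol already urges caution with null results, admits low power for rarer outcomes in sections 3.7 and 5.0, and considers a nested case-control study in section 4.5. So it cannot be said that nulls will be over-read. The caveat is about rare outcomes, however, while RR 1.2 at 3% risk also loses power.
- A second column might have been lost when the PDF was read. This cannot be excluded, but the header and 18 single-value rows are consistent, and every printed value fits 0.05.

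**Conclusion.** The point holds as a reporting error in section 3.7 with a limited numerical effect. The 0.01 results are announced and absent, Table 6 is an unlabelled two-sided 0.05 table, and no figure reflects the section 4.4 correction.

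The threshold matters for rare outcomes and for RR 1.2. In the stated direction, the largest falls from 0.05 to 0.05/15 are 66.5 to 23.3 (5,000, 0.5%, RR 0.5), 55.5 to 21.3 (5,000, 3%, RR 1.2) and 83.4 to 51.5 (10,000, 3%, RR 1.2). It hardly matters for 3% and 10% outcomes at RR 0.5 or 2.0.

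This rests on two-sided tests, independent groups and a family of 15 primary outcomes. The protocol gives no matching correlation, so the effect of matching is not quantified. If all 23 outcomes form the family, the floor is 0.05/23 = 0.0022 and power for 10,000, 0.5%, RR 0.5 falls to 60.0% instead of 65.8%.

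**What to change.** Recalculate Table 6 once:

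1. Apply the RR in the stated direction (vaccinated risk = RR × background risk). Without this, new columns would carry the inversion forward.
2. Label the 0.05 column as two-sided and uncorrected.
3. Print the announced 0.01 column.
4. Add a column at 0.05/m as the lower bound under the planned correction, and name the family of m tests.
5. State that power under Benjamini-Hochberg lies between the 0.05/m and 0.05 columns, and that null results will be read against that range.
6. Amend the worked sentence about the 94% to match.

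The cost is one table and a few sentences; data, design and analysis are unchanged. The drawback is that some stated power figures become less favourable.

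### Table 6 applies the relative risk upside down: power for RR 0.5 at 0.5% risk is about 66%, not 94%, and power to detect harm is understated

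*Protocol*

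**What the plan says.** Section 3.7 sets up the calculation "with the relative risk of an event occurring post-vaccination set at 0.5, 1.2 and 2.0". The baseline risks are grouped: "Outcomes can be grouped as frequent (risk approximately 10%), moderate (approximately 3%), and rare (approximately 0.5"%). The source is given as "Risk estimates for each adverse outcome are provided in Table 2", and the corresponding column of Table 2 is headed as the estimated background risk of each outcome. Two sizes are considered: 5,000 vaccinated against 15,000 controls, and, "by end of 2022, data available for 10,000 vaccinated pregnant women", with 30,000 controls in Table 6.

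The text works one case: "The power to detect a relative risk of 0.5, based on 5000 vaccinated pregnant woman against 15000 controls (ratio 1:3"), at an event risk of 0.5%, is put at 94%. It is interpreted as follows: "This means that the study has a 94% chance of having a p-value of less than 5"% if a true difference exists. Table 6 repeats the 94% and gives 10% for RR 1.2 and 66% for RR 2.0 in the same block. The section takes 80% as the acceptable level, says null results need caution where power is low, and adds: "It is acknowledged that the study may be under-powered to identify rarer outcomes".

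**The concern.** The ordering of the two figures is impossible under the stated definitions. With a background risk of 0.5%, RR 2.0 compares 1.0% with 0.5%, a gap of 0.5 points. RR 0.5 compares 0.25% with 0.5%, a gap of 0.25 points. The standard error is larger for the doubling, but by much less than a factor of two, so the doubling must have the higher power. Table 6 shows the reverse.

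This is a safety study, so relative risks above 1 are the ones that matter, and the protocol ties the reading of null results to these power figures. A reader using Table 6 would regard the study as short of power for a doubling of a 0.5% outcome and discount a null finding there. Several Table 2 outcomes lie close to that row: stillbirth and severe microcephaly (0.4%), very low Apgar (0.5%) and extended perinatal mortality (0.6%). The same reader would believe the study well able to detect a halving, which it is not.

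**Working it through.** **Inputs.** Group sizes, relative risks and baseline risks are those of section 3.7 and Table 6. The baseline risk p is the risk in controls, because Table 2 calls it the background risk. The worked example uses a 5% level. Sidedness is not stated, and two-sided is assumed.

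**Formula.** With n1 vaccinated at risk p1, n2 controls at risk p2 and pooled risk P = (n1·p1 + n2·p2)/(n1 + n2):

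- SE0 = √[P(1−P)(1/n1 + 1/n2)]
- SE1 = √[p1(1−p1)/n1 + p2(1−p2)/n2]
- power = Φ[(|p1−p2| − 1.96·SE0)/SE1]

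**Reproducing the printed 94%.** It appears only if RR 0.5 is applied as p1 = p/RR = 0.5%/0.5 = 1.0%, against p2 = 0.5%:

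- P = (50 + 75)/20,000 = 0.00625; SE0 = 0.001287; SE1 = 0.001520
- (0.005 − 1.96 × 0.001287)/0.001520 = 1.63; power 94.8%

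That comparison is a doubling, so 94.8% is the power for RR 2.0.

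**RR 0.5 as defined.** p1 = 0.5% × 0.5 = 0.25%, p2 = 0.5%:

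- P = (12.5 + 75)/20,000 = 0.004375; SE0 = 0.001078; SE1 = 0.000911
- (0.0025 − 1.96 × 0.001078)/0.000911 = 0.425; power 66.5%

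**All cells not at about 100% throughout** (power, %):

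| Vaccinated | Risk | RR label | Printed | p1 = p/RR | p1 = p×RR (as defined) |
|---|---|---|---|---|---|
| 5,000 | 0.5% | 0.5 | 94 | 94.8 | 66.5 |
| 5,000 | 0.5% | 1.2 | 10 | 10.1 | 14.4 |
| 5,000 | 0.5% | 2.0 | 66 | 66.5 | 94.8 |
| 5,000 | 3% | 1.2 | 45 | 44.7 | 55.5 |
| 5,000 | 10% | 1.2 | 94 | 94.2 | 97.5 |
| 10,000 | 0.5% | 0.5 | 100 | 99.9 | 94.1 |
| 10,000 | 0.5% | 1.2 | 17 | 16.9 | 23.3 |
| 10,000 | 0.5% | 2.0 | 94 | 94.1 | 99.9 |
| 10,000 | 3% | 1.2 | 75 | 74.5 | 83.4 |

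The other nine cells are at about 100% in either direction. The inverted column matches every printed value within one point. The rows labelled 0.5, 1.2 and 2.0 therefore describe relative risks of 2.0, 0.83 (1/1.2) and 0.5.

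**Other readings tried for 5,000 vaccinated.**

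- *p is the vaccinated risk and the control risk is p/RR:* 74.6% where 66 is printed, and 48.3% where 45 is printed.
- *Control risk is p×RR, or the group sizes are swapped:* 74.6% where 94 is printed.
- *Level 0.01:* at 0.5% risk and RR 0.5, 38.1% in the stated direction and 86.6% inverted, where 94 is printed.
- *Continuity-corrected, unpooled, arcsine, Wald and exact versions in the stated direction:* 61% to 78% two-sided where 94 is printed; the one-sided test gives 78.8%.

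**The case against.** The strongest reply is that little depends on the table. The 5,000 and 10,000 come from expected data availability rather than a power target, and no analysis rule cites a cell. For harm the error is conservative. The only overstated cells are the two for RR 0.5 at 0.5% risk, a protective effect. All of this is true. It bears on how much harm the error does, and does not make the figures right.

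A second reply is that 95% is itself generous, because it ignores the matching, covariate adjustment and the multiplicity correction planned in section 4.4. This also stands. At level 0.01, which section 3.7 announces beside 0.05, RR 2.0 at 0.5% with 5,000 vaccinated has 86.6%, and RR 1.2 at 3% with 10,000 has 65%. If the family were the 15 primary outcomes of Table 2 (an assumption, since the protocol does not fix the family), the strictest Benjamini–Hochberg step, 0.05/15, gives about 79% for the first of these. But the printed figures carry the same simplifications, so the comparison of printed with corrected values is like for like.

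Third, the caution about rare outcomes remains true in part after correction. RR 1.2 at 0.5% has only 14% and 23% power at the two sizes. For outcomes rarer than the 0.5% row, RR 2.0 has 55.5% and 81% for venous thromboembolism (0.15%), and 66% and 90% for neonatal death (0.2%). The protocol never says outright that it is under-powered for a doubling of a 0.5% outcome. A reader infers that from the 66% and the 80% convention.

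**Conclusion.** The error is real. As labelled, 9 of the 18 cells in Table 6 are wrong, and so is the only worked example. Power for RR 0.5 at 0.5% risk with 5,000 vaccinated is about 66%, not 94%; for RR 2.0 it is about 95%, not 66%. Seven of the 12 cells for RR 1.2 and 2.0 are understated, and the other five are at about 100% either way. Three conclusions change sides of the protocol's 80% convention: the two harm cells (66 to 95 and 75 to 83) move above it, and the worked example moves below it.

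These values rest on an unmatched two-proportion test at two-sided 5% with Table 2 risks as control risks. Other tests shift them by a few points and do not restore 94%. The original software and formula cannot be identified from the protocol, but inversion of the relative risk is the only reading tried that fits every cell.

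**What to change.** - Recompute Table 6 with vaccinated risk equal to background risk times RR, and state in the table that RR is vaccinated over unvaccinated.
- Correct the worked sentence to either RR 0.5 with 66% or RR 2.0 with 95%. The second serves a safety study better.
- State the level and sidedness behind the table. Section 3.7 announces 0.05 and 0.01, but one set of powers is shown and it matches 0.05.
- Make the under-powering statement specific: adequate for a doubling at 0.5% (before any multiplicity correction), not adequate for RR 1.2 at that risk, and limited for rarer outcomes at 5,000 vaccinated.
- Optionally, add a row at 0.15% to 0.2%, so that venous thromboembolism and neonatal death are not read off the 0.5% row.

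The cost is one table and a few sentences of protocol text. Data, design and study size are unaffected.
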